11.4 Measurement of Effect

11.41 Target Lesions & Target Lymph Nodes

- Measurable lesions (as defined in Section 11.21) up to a maximum of 5 lesions, representative of all involved organs, should be identified as “Target Lesions” and recorded and measured at baseline. These lesions can be non-nodal or nodal (as defined in 11.21), where no more than 2 lesions are from the same organ and no more than 2 malignant nodal lesions are selected.

Note: If fewer than 5 target lesions and target lymph nodes are identified (as there often will be), there is no reason to perform additional studies beyond those specified in the protocol to discover new lesions.

- Target lesions and target lymph nodes should be selected on the basis of their size, be representative of all involved sites of disease, but in addition should be those that lend themselves to reproducible repeated measurements. It may be the case that, on occasion, the largest lesion (or malignant lymph node) does not lend itself to reproducible measurements in which circumstance the next largest lesion (or malignant lymph node) which can be measured reproducibly should be selected.
- Baseline Sum of Dimensions (BSD): A sum of the longest diameter for all target lesions plus the sum of the short axis of all the target lymph nodes will be calculated and reported as the baseline sum of dimensions (BSD). The BSD will be used as reference to further characterize any objective tumor response in the measurable dimension of the disease.
- Post-Baseline Sum of the Dimensions (PBSD): A sum of the longest diameter for all target lesions plus the sum of the short axis of all the target lymph nodes will be calculated and reported as the post-baseline sum of dimensions (PBSD). If the radiologist is able to provide an actual measure for the target lesion (or target lymph node), that should be recorded, even if it is below 0.5 cm. If the target lesion (or target lymph node) is believed to be present and is faintly seen

but too small to measure, a default value of 0.5 cm should be assigned. If it is the opinion of the radiologist that the target lesion or target lymph node has likely disappeared, the measurement should be recorded as 0 cm.

- The minimum sum of the dimensions (MSD) is the minimum of the BSD and the PBSD.

11.42 Non-Target Lesions & Non-Target Lymph Nodes

Non-measurable sites of disease (Section 11.22) are classified as non-target lesions or non-target lymph nodes and should also be recorded at baseline. These lesions and lymph nodes should be followed in accord with 11.433.

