11.21 Measurable Disease

- 11.211 A non-nodal lesion is considered measurable if its longest diameter can be accurately measured as ≥ 2.0 cm with chest x-ray, or as ≥ 1.0 cm with CT scan, CT component of a PET/CT, or MRI.
- 11.212 A superficial non-nodal lesion is measurable if its longest diameter is ≥ 1.0 cm in diameter as assessed using calipers (e.g. skin nodules) or imaging. In the case of skin lesions, documentation by color photography, including a ruler to estimate the size of the lesion, is recommended.
- 11.213 A malignant lymph node is considered measurable if its short axis is ≥ 1.5 cm when assessed by CT scan (CT scan slice thickness recommended to be no greater than 5 mm).

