11.22 Non-Measurable Disease

- 11.221 All other lesions (or sites of disease) are considered non-measurable disease, including pathological nodes (those with a short axis ≥ 1.0 to < 1.5 cm). Bone lesions, leptomeningeal disease, ascites, pleural/pericardial effusions, lymphangitis cutis/pulmonis, inflammatory breast disease, and abdominal masses (not followed by CT or MRI), are considered as non-measurable as well.

Note: 'Cystic lesions' thought to represent cystic metastases can be considered as measurable lesions, if they meet the definition of measurability described above. However, if non-cystic lesions are present in the same patient, these are preferred for selection as target lesions. In addition, lymph nodes that have a short axis < 1.0 cm are considered non-pathological (i.e., normal) and should not be recorded or followed.

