11.43 Response Criteria

11.431 All target lesions and target lymph nodes followed by CT/MRI/PET-CT/Chest X-ray/physical examination must be measured on re-evaluation at evaluation times specified in Section 11.1. Specifically, a change in objective status to either a PR or CR cannot be done without re-measuring target lesions and target lymph nodes.

Note: Non-target lesions and non-target lymph nodes should be evaluated at each assessment, especially in the case of first response or confirmation of response. In selected circumstances, certain non-target organs may be evaluated less frequently. For example, bone scans may need to be repeated only when complete response is identified in target disease or when progression in bone is suspected.

11.432 Evaluation of Target Lesions

- Complete Response (CR): All of the following must be true:
 - a. Disappearance of all target lesions.
 - b. Each target lymph node must have reduction in short axis to <1.0 cm
- Partial Response (PR): At least a 30% decrease in PBSD (sum of the longest diameter for all target lesions plus the sum of the short axis of all the target lymph nodes at current evaluation) taking as reference the BSD (*see* Section 11.41).
- Progression (PD): At least one of the following must be true:
 - a. At least one new malignant lesion, which also includes any lymph node that was normal at baseline (< 1.0 cm short axis) and increased to ≥ 1.0 cm short axis during follow-up.

- b. At least a 20% increase in PBSD (sum of the longest diameter for all target lesions plus the sum of the short axis of all the target lymph nodes at current evaluation) taking as reference the MSD (Section 11.41). In addition, the PBSD must also demonstrate an absolute increase of at least 0.5 cm from the MSD.
- c. See Section 11.32 for details in regards to the requirements for PD via FDG-PET imaging.

- Stable Disease (SD): Neither sufficient shrinkage to qualify for PR, nor sufficient increase to qualify for PD taking as reference the MSD.

11.433 Evaluation of Non-Target Lesions & Non-target Lymph Nodes

- Complete Response (CR): All of the following must be true:
 - a. Disappearance of all non-target lesions.
 - b. Each non-target lymph node must have a reduction in short axis to <1.0 cm.
- Non-CR/Non-PD: Persistence of one or more non-target lesions or non-target lymph nodes.
- Progression (PD): At least one of the following must be true:

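### Section 11.42 gives no class to measurable lesions left unselected as targets, so CR can be assigned while they persist, and CR, PR or SD while they progress

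*Combined protocol and SAP*

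**What the plan says.** All references are to the combined protocol and SAP.

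- **Measurability (11.21)** depends on size and modality: "A non-nodal lesion is considered measurable if its longest diameter can be accurately measured as" the stated thresholds. Selection as a target plays no part.
- **Non-measurable disease (11.22)** is the remainder: "All other lesions (or sites of disease) are considered non-measurable disease". For nodes the section gives a short-axis range of 1.0 cm to below 1.5 cm.
- **Targets (11.41)** are measurable lesions, "up to a maximum of 5 lesions, representative of all involved organs, should be identified as “Target Lesions” and recorded and measured at baseline", where "no more than 2 lesions are from the same organ and no more than 2 malignant nodal lesions are selected". If the largest lesion cannot be measured reproducibly, "the next largest lesion (or malignant lymph node) which can be measured reproducibly should be selected". Section 11.22 adds for cystic lesions that "if non-cystic lesions are present in the same patient, these are preferred for selection as target lesions".
- **Non-targets (11.42)**: "Non-measurable sites of disease (Section 11.22) are classified as non-target lesions or non-target lymph nodes and should also be recorded at baseline".
- **Status (11.432 to 11.44)**: the first condition for target CR is "Disappearance of all target lesions". Non-target CR and PD refer to non-target lesions and nodes. The overall status table combines target status, non-target status and new sites.
- **Use**: tumor response (16.321) is a CR or PR on two consecutive evaluations. Progression-free survival (16.322) runs to documented progression or death. Sections 7.4, 13.1 and 13.2 make continuation depend on whether the patient has PD.

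**The concern.** A measurable lesion can go unselected in three ways: it lies beyond a cap, it is passed over as not reproducibly measurable, or it is cystic and others are preferred. Section 11.42 does not take it up, because it refers only to disease that fails the size rules. No rule then requires the lesion to be recorded or followed, and no change in it can alter the written objective status.

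The exposed patients have more than 2 measurable lesions in one organ, more than 2 measurable nodes, more than 5 measurable lesions in all, or a lesion passed over for the other two reasons. For them a CR may be declared with measurable disease still present, and progression confined to the unselected lesions may go uncounted. Both secondary imaging endpoints use this status, and so do the decisions on continuing treatment.

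**Working it through.** The plan states no figure on this point, so there is none to reproduce. The check follows one lesion through the definitions and then applies the status rules to two illustrative patients. The lesion sizes are assumptions, not taken from the documents.

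**Step 1: classify an unselected measurable lesion.** Take a third node with a short axis of 1.8 cm when two nodes are already targets.

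- Target? No: the node cap in 11.41 is reached.
- Non-measurable under 11.22? No: 1.8 cm is at least 1.5 cm, so it meets 11.21 and lies outside the 11.22 node range.
- Non-target under 11.42? No: that class is filled from 11.22.
- New? No: it was present at baseline.

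No input of the 11.44 table remains for it.

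**Step 2: persistence.** Assume six lung metastases of 2.0 cm and no other disease. Two are targets (2 × 2.0 = 4.0 cm) and four are unclassified. The two targets vanish and the four remain.

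- As written: target CR, no recorded non-target disease left, no new site. Overall status is CR, taking the non-target condition as met when none is recorded.
- With the four as non-target: target CR with non-CR/non-PD. Overall status is PR.
- Consequence: CR and PR both count as response under 16.321 once confirmed, and both continue treatment under 13.1. Only the label changes.

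**Step 3: growth with stable targets.** Same patient. The targets stay at 4.0 cm and the other four grow from 2.0 to 4.0 cm each.

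- Total at baseline: 6 × 2.0 = 12 cm.
- Total at follow-up: 2 × 2.0 + 4 × 4.0 = 20 cm.
- Change: 20/12 − 1 = +67%.
- As written: the target sum is unchanged, so overall status is SD.
- With the four as non-target: PD if the growth is judged unequivocal under 11.433.

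**Step 4: growth with responding targets.** Assume five targets of 4, 3, 3, 3 and 2 cm (sum 15 cm) that shrink to 2.5, 2, 2, 2 and 1.5 cm (sum 10 cm). Two unselected lesions grow from 2.0 to 4.0 cm each.

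- Targets: 10/15 − 1 = −33.3%, beyond the 30% decrease required for PR.
- Unselected: 4.0 to 8.0 cm, +100%.
- All seven together: (10 + 8)/(15 + 4) − 1 = 18/19 − 1 = −5.3%.
- As written: PR, if recorded non-target disease is CR or non-CR/non-PD and there is no new site.
- With the two as non-target: PD if unequivocal, but 11.433 cautions that non-target progression should not normally override target status, so PR could still stand.

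**Step 5: weight of one patient.** With the 35 evaluable patients of 16.22, one changed classification moves the response rate by 1/35 = 2.9 percentage points.

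**The case against.** The strongest reply is that Section 11.0 adopts the RECIST 1.1 guideline, which the reference list cites, and that 11.42 never says nothing else may be non-target. Assessors may fill the gap from the guideline. Whether it does so cannot be checked from these documents. What can be read is that the study works from a dated protocol template, which the note to 11.44 ties to data collection and analysis, and nothing in that template classifies these lesions. The general reference does not make up for the missing sentence.

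There are partial safeguards. The scheduled scans still show the lesions. The FDG-PET algorithm in 11.32 mentions pre-existing sites without limiting them to listed ones, but applies only where PET is used. Symptomatic deterioration (11.45) needs clinical decline and would miss silent growth.

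The growth case is also narrow. Unselected lesions must progress while targets, chosen by size and to represent the involved sites, are stable or shrinking, with no new lesion. This stands and limits how often the gap matters.

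A reader might infer more than the text supports:

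- **Persistence makes PR or SD wrong.** It does not: both allow residual disease. Persistence conflicts with CR alone.
- **An overcalled CR creates a responder or keeps a patient on treatment.** It does neither, as Step 2 shows.
- **Unrecorded lesions will later be taken for new ones.** This is speculative: baseline CT or MRI is required with the same method throughout, and such an error would produce PD, the opposite of missed PD.

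**Conclusion.** The concern holds in this form. On the written rules, measurable lesions and nodes not selected as targets cannot affect objective status. CR can be assigned where PR is correct, with no effect on response or continuation. CR, PR or SD can also be assigned while those lesions unequivocally progress. The second effect can lengthen progression-free survival, raise the response rate and alter decisions tied to PD.

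Its size cannot be stated, because the documents do not give the share of patients with unselected measurable disease. The illustrations show what the rules permit, not how often it happens. The conclusion assumes that Section 11 is applied as written.

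A reader might infer that the trial's main result is at risk. It is not: 12-month overall survival does not use these criteria. Response and progression-free survival are estimated without a stated hypothesis test. The amendment is still worth making, because a stated rule can give a wrong status and the correction is small.

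**What to change.** Amend Section 11.42 to say that all other disease present at baseline is classified as non-target, recorded at baseline and followed under 11.433. This means both the non-measurable sites of 11.22 and any measurable lesions or lymph nodes not selected as targets under 11.41. Sections 11.433 and 11.44 can stay as they are: growth in these lesions would count as PD only if it meets the existing standard of unequivocal progression, so not every increase would change the status.

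The cost is a few more lines on the baseline RECIST form, with possibly slightly fewer CR calls and slightly earlier PD. No scans are added, and the sample size and dose rules do not change.

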11.43 Response Criteria

11.431 All target lesions and target lymph nodes followed by CT/MRI/PET-CT/Chest X-ray/physical examination must be measured on re-evaluation at evaluation times specified in Section 11.1. Specifically, a change in objective status to either a PR or CR cannot be done without re-measuring target lesions and target lymph nodes.

Note: Non-target lesions and non-target lymph nodes should be evaluated at each assessment, especially in the case of first response or confirmation of response. In selected circumstances, certain non-target organs may be evaluated less frequently. For example, bone scans may need to be repeated only when complete response is identified in target disease or when progression in bone is suspected.

11.432 Evaluation of Target Lesions

- Complete Response (CR): All of the following must be true:
 - a. Disappearance of all target lesions.
 - b. Each target lymph node must have reduction in short axis to <1.0 cm
- Partial Response (PR): At least a 30% decrease in PBSD (sum of the longest diameter for all target lesions plus the sum of the short axis of all the target lymph nodes at current evaluation) taking as reference the BSD (*see* Section 11.41).
- Progression (PD): At least one of the following must be true:
 - a. At least one new malignant lesion, which also includes any lymph node that was normal at baseline (< 1.0 cm short axis) and increased to ≥ 1.0 cm short axis during follow-up.

- b. At least a 20% increase in PBSD (sum of the longest diameter for all target lesions plus the sum of the short axis of all the target lymph nodes at current evaluation) taking as reference the MSD (Section 11.41). In addition, the PBSD must also demonstrate an absolute increase of at least 0.5 cm from the MSD.
- c. See Section 11.32 for details in regards to the requirements for PD via FDG-PET imaging.

- Stable Disease (SD): Neither sufficient shrinkage to qualify for PR, nor sufficient increase to qualify for PD taking as reference the MSD.

11.433 Evaluation of Non-Target Lesions & Non-target Lymph Nodes

- Complete Response (CR): All of the following must be true:
 - a. Disappearance of all non-target lesions.
 - b. Each non-target lymph node must have a reduction in short axis to <1.0 cm.
- Non-CR/Non-PD: Persistence of one or more non-target lesions or non-target lymph nodes.
- Progression (PD): At least one of the following must be true:
 - a. At least one new malignant lesion, which also includes any lymph node that was normal at baseline (< 1.0 cm short axis) and increased to ≥ 1.0 cm short axis during follow-up.
 - b. Unequivocal progression of existing non-target lesions and non-target lymph nodes. (NOTE: Unequivocal progression should not normally trump target lesion and target lymph node status. It must be representative of overall disease status change.)
 - c. See Section 11.32 for details in regards to the requirements for PD via FDG-PET imaging.

11.44 Overall Objective Status

The overall objective status for an evaluation is determined by combining the patient's status on target lesions, target lymph nodes, non-target lesions, non-target lymph nodes, and new disease as defined in the following tables:

For Patients with Measurable Disease

Target Lesions & Target Lymph Nodes	Non-Target Lesions & Non-Target Lymph Nodes	New Sites of Disease	Overall Objective Status
CR	CR	No	CR
CR	Non-CR/Non-PD	No	PR
PR	CR Non-CR/Non-PD	No	PR
CR/PR	Not All Evaluated*	No	PR**
SD	CR Non-CR/Non-PD Not All Evaluated*	No	SD
Not all Evaluated	CR Non-CR/Non-PD Not All Evaluated*	No	Not Evaluated (NE)
PD	Unequivocal PD CR Non-CR/Non-PD Not All Evaluated*	Yes or No	PD
CR/PR/SD/PD/Not all Evaluated	Unequivocal PD	Yes or No	PD
CR/PR/SD/PD/Not all Evaluated	CR Non-CR/Non-PD Not All Evaluated*	Yes	PD

*See Section 11.431

** NOTE: This study uses the protocol RECIST v1.1 template dated 2/16/2011. For data collection and analysis purposes the objective status changed from SD to PR in the MCCC protocol RECIST v1.1 template as of 2/16/2011 and to match RECIST v1.1 requirements.

For Patients with Non-Measurable Disease Only:

Non-Target Lesions & Non-Target Lymph Nodes	New Sites of Disease	Overall Objective Status
CR	No	CR
Non-CR/Non-PD	No	Non-CR/Non-PD
Not All Evaluated*	No	Not Evaluated (NE)
Unequivocal PD	Yes or No	PD
Any	Yes	PD

*See Section 11.431

- 11.45 Symptomatic Deterioration: Patients with global deterioration of health status requiring discontinuation of treatment without objective evidence of disease progression at that time, and not either related to study treatment or other medical conditions, should be reported as PD due to “symptomatic deterioration.” Every effort should be made to document the objective progression even after discontinuation of treatment due to symptomatic deterioration. A patient is classified as having PD due to “symptomatic deterioration” if any of the following occur that are not either related to study treatment or other medical conditions:
- Worsening of tumor-related symptoms.
 - Decline in performance status of >1 level on ECOG scale.

12.0 Descriptive Factors

- 12.1 Prior treatment for metastatic non clear cell renal cell cancer: none vs. sorafenib vs. sunitinib vs. temsirolimus vs. interferon vs bevacizumab vs everolimus vs. other metastatic renal cell cancer treatments.
- 12.2 Non-clear cell metastatic renal cell cancer histology: chromophilic vs. chromophobic vs. oncocytic vs. collecting duct vs. sarcomatoid differentiation.

13.0 Treatment/Follow-up Decision at Evaluation of Patient

- 13.1 Patients who are CR, PR, or SD will continue treatment per protocol.
- 13.2 Patients who develop PD while receiving therapy will go to the event-monitoring phase.
- 13.3 Patients who go off protocol treatment for reasons other than PD will go to the event-monitoring phase per Section 18.0.
- 13.4 Patients who develop non-CNS PD at any time should go to event monitoring.
- 13.5 A patient is deemed *ineligible* if after registration, it is determined that at the time of registration, the patient did not satisfy each and every eligibility criteria for study entry. The patient may continue treatment off-protocol at the discretion of the physician as long as there are no safety concerns, and the patient was properly registered. The patient will go directly to the event-monitoring phase of the study (or off study, if applicable).
- If the patient received treatment, all data up until the point of confirmation of ineligibility must be submitted. Event monitoring will be required per Section 18.0 of the protocol.
 - If the patient never received treatment, on-study material must be submitted. Event monitoring will be required per Section 18.0 of the protocol.
- 13.6 A patient is deemed a *major violation*, if protocol requirements regarding treatment in cycle 1 of the initial therapy are severely violated that evaluability for primary end point is questionable. All data up until the point of confirmation of a major violation must be submitted. The patient will go directly to the event-monitoring phase of the study. The patient may continue treatment off-protocol at the discretion of the physician as long as there are no safety concerns, and the patient was properly registered. Event monitoring will be required per Section 18.0 of the protocol.

- 13.7 A patient is deemed a cancel if he/she is removed from the study for any reason before any study treatment is given. On-study material and the End of Active Treatment/Cancel Notification Form must be submitted. The patient will go directly to the event-monitoring phase of the study, and event monitoring will be required per Section 18.0 of the protocol.

14.0 Body Fluid Biospecimens

Note: As of addendum 7 all blood and urine correlatives discussed in section 14 are no longer being collected at any of the Mayo Clinic sites. All blood and urine specimens collected prior to the implementation of addendum 7 will be stored and utilized in the manner described above if and when funding becomes available.

14.1 Summary Table of Research Blood and Body Fluid Specimens to be Collected for this Protocol*

Correlative Study	Mandatory or Optional	Specimen to Collect	Type of Collection Tube (color of tube top)	Volume to collect per tube (# of tubes to collect)	Prior to Registration (≤14 days)	Cycle 3 Day 1	Cycle 5 Day 1	Process at site? (Yes or No)	Temperature Conditions for Storage /Shipping
Bank for Future Proteomics, Metabolomics, and Genomics Studies (Section 14.21)	Mandatory	Whole Blood	EDTA (purple top)	4, 6 mL (2)	X	X	X	No	Frozen / Dry Ice
Bank for Future Proteomics, Metabolomics, and Genomics Studies (Section 14.21)	Mandatory	Whole Blood	Sodium Citrate (blue top)	5 mL (1)	X	X	X	No	Frozen / Dry Ice
Bank for Future Proteomics, Metabolomics, and Genomics Studies (Section 14.22)	Mandatory	Whole Blood	SST (black/red top)	8.5 mL (1)	X	X	X	No	Frozen / Dry Ice
Bank for Future Proteomics, Metabolomics, and Genomics Studies (Section 14.23)	Mandatory	Whole Blood	Paxgene	5 mL (1)	X	X	X	No	Frozen / Dry Ice
Bank for Future Proteomics, Metabolomics, and Genomics Studies (Section 14.24)	Mandatory	Urine	-	10-15 mL	X	X	X	No	Frozen / Dry Ice

*Research Blood and Body fluid specimens are funded by Mayo

